### Stopping plans

Any participant who develops a serum calcium levels  $\geq 10.6$  meq/L and/or a 25(OH)D level  $\geq 80$  ng/ml or symptoms of vitamin D intoxication (e.g. bone pain, nausea or vomiting) will stop treatment but they will continue to be monitored in the study through week 12 when serum calcium and 25(OH)D levels will be measured at the end of the study. The study will continue until participants have been followed for 12 weeks.

### VIII. Analysis Plan

This feasibility study will examine multiple aspects of the pilot data including the total number of persons enrolled vs. number of total persons identified as eligible. Pill counts will be done at the 6 and 12 week visit to assess compliance with vitamin D and calcium supplementation. The percentage of participants taking 80% or more of the vitamin D3 supplement and the calcium supplement will be determined. The number of participants reporting symptoms and all adverse events will be quantified. Repeated measures analysis of variance models will be used to assess change in the outcome measures including systolic and diastolic blood pressure, vitamin D measures, parathyroid hormone levels and 24-hour urine calcium excretion values.

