**Abstract:**

I. Abstract

Adequate levels of vitamin D are essential for bone health at all ages but low levels of vitamin D may also negatively impact other aspects of health such as blood pressure. We have previously shown that adults with African ancestry living near the equator have much higher levels of vitamin D and higher levels of blood pressure compared to adults with African ancestry living in the Chicago area. Multiple clinical trials have examined vitamin D supplementation for reducing blood pressure levels **but very few studies have focused on adults with African ancestry and low vitamin D levels**. In addition, most previous clinical trials have not addressed calcium intake. While vitamin D may modulate blood pressure via its actions on activation of the renin angiotensin system, it is also possible that vitamin D mediates blood pressure via its effects on gastrointestinal calcium absorption. This pilot study is a one arm study which will assess the safety and feasibility of supplementing 15 young adults with African ancestry and low vitamin D levels with 5,000 IU of Cholecalciferol (vitamin D3) combined with 1000 mg of elemental calcium daily for 12 weeks. Participants will be recruited from the Maywood and surrounding areas with flyers and brochures. We will also contact previous participants of the Modeling the Epidemiologic Study/Vitamin D Ancillary Study by phone and letters. At baseline, all participants will have blood pressure measured and a fasting serum and 24-hour urine specimen will be collected for measurement of calcium, parathyroid hormone and vitamin D levels and urinary calcium excretion. Repeat visits will be completed at 6 and 12 weeks of follow-up to again measure resting blood pressure and serum calcium and vitamin D levels and urinary calcium excretion. The overall goal is to collect pilot data to help design a larger trial of vitamin D and calcium supplementation for lowering blood pressure in young adults with African ancestry.

II. Background and Significance

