### Inclusion Criteria

1. Age 25-45 years
2. Self-reported race/ethnicity African American
3. BMI  $\geq$  25 kg/m^2
4. Total 25(OH)D levels  $<$  20 ng/ml (50 nmol/L)
5. No use of vitamin D supplements within past 30 days of the screening visit
6. Able to provide written informed consent
7. Willing to take a vitamin D supplement daily for 12 weeks
8. Willing to return for follow-up visits to measure blood pressure and provide a blood sample to measure vitamin D and serum calcium
9. No current use of blood pressure lowering medications
10. Systolic blood pressure  $\geq$  120 mmHg and diastolic blood pressure  $\geq$  60 mmHg
11. Estimated calcium intake  $<$  1000 mg/day

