## Exclusion Criteria

1. Medical history of chronic disease that affect gastrointestinal absorption of vitamin D: Crohn's disease, cystic fibrosis, and celiac disease
2. Use of medications which may affect total 25(OH)D levels: antiepileptic drugs, steroids, bile acid sequestrants, lipase inhibitors, orlistat
3. Current use of vitamin D supplements or use in past 8 weeks and unwillingness to discontinue for at least 1 month prior to study enrollment
4. History of kidney stones or hypercalciuria ( > 250 mg urinary calcium excretion)
5. Fasting serum calcium  $\geq$  10.2 mg/dl at the screening visit
6. Average systolic blood pressure  $\geq$  140 mmHg
7. Average diastolic blood pressure  $\geq$  90 mmHg
8. Presence of active malignancy, active thyroid disease or sarcoidosis
9. Pregnant or planning a pregnancy or breastfeeding
10. Estimated glomerular filtration rate (based on serum creatinine level) is < 60 ml/min/1.73 m^2 based on the Modification of Diet in Renal Disease formula
11. Enrolled in a clinical trial
12. Any history of a heart attack, stroke, angioplasty or coronary artery bypass grafting or physician diagnosis of heart failure

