### d. Study outcomes/endpoints:

#### a. Blood pressure

Seated blood pressure and pulse are measured at the screening visit, enrollment visit and at 6 and 12 week follow-up visits in the clinic using an appropriate sized cuff after a rest period using an automated device (Omron). Arm circumference will be measured using a standard flexible tape measure. The cuff size will be determined based on arm circumference. Participants will be instructed to not smoke for 30 minutes prior to the exam and to not drink any caffeinated beverages for one hour prior to the exam. All participants will be instructed to fast for 4 hours prior to the exam. Participants will be instructed to empty their bladder prior to the exam. Participants will be seated for 5 minutes prior to blood pressure measurement. Blood pressure will be measured three times in one minute intervals using an Omron

automatic device with the study staff not in the room. The average of these three recordings will be recorded as the mean blood pressure.

b. Total 25(OH)D and 1,25(OH)2D levels

Total 25[OH]D and 1,25[OH]2D: Total 25[OH]D and 1,25[OH]2D will be measured with the use of liquid chromatography-tandem mass spectrometry (LC-MS/MS)(inter-assay coefficient of variation for 25[OH]D3 = 4.8% and for 1,25[OH]2D = 8.8%). The assay will measure total 25[OH]D, including 25[OH]D3 and 25[OH]D2, calibrated to standards provided by the National Institute of Standards and Technology. We will provide all potential participants who are screened or enrolled with the results of their vitamin D results. For screening purposes, 25(OH)D will be measured in specimens collected at the screening visit and testing will be done by Quest. Then 25(OH)D will be measured at Quest in banked specimens from the screening visit and from visits 6 and 12 weeks after the enrollment visit. 1,25(OH)2D will be measured in banked specimens obtained at the screening visit and in blood specimens obtained at the visit 12 weeks after enrollment.

c. Free 25(OH)D

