Screening visits will occur in the CTRE clinic on the 1st floor and written informed consent for the screening visit and study will be obtained by research staff or investigators. At the screening visit, participants will provide written informed consent. Participants will also be asked to provide written informed consent for their serum and urine specimens to be placed in a biorepository for future studies. Participating in the biorepository is optional and will not affect their ability to participate in the screening exam or their overall eligibility to participate in the BBC and Vitamin D study. The screening visit will take ninety minutes to complete. Potential participants will be instructed to fast for at least four hours prior to the screening exam. All laboratory tests taken during the screening visit will be for research purposes and will not be part of standard care. During a screening visit, a research investigator will review the past medical history and any medication use to ensure the participant meets all inclusion and exclusion criteria. Resting blood pressure will be taken per protocol and height and weight will be measured. A fasting blood sample (15 ml) will be collected from the potential participant. Blood will be sent to Quest for measurement of serum creatinine and calcium and vitamin D. Participants will be asked to collect a 24-hour urine collection to measure urinary calcium excretion. Urine calcium will be measured by Quest. We anticipate that we will need to screen 60 adults to identify 15 individuals who are eligible for the study. Data collected from any individual who is found not be eligible for the study will be kept in a secure database (REDCAP) on a secure Loyola drive. For participants who do not enroll in the BBC and Vitamin D study, all banked specimens will be discarded unless they provided written informed consent to participate in Loyola's biorepository.

[figure not shown]

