Once the lab values for the potential participant have been reported to the investigators, then study eligibility may be determined. Individuals will be contacted by phone or via mailed letter regarding study eligibility. For those individuals who are eligible to participate in the study, an enrollment visit will be scheduled within 28 days of the screening visit. The enrollment visit and all subsequent visits will be held at Loyola University Chicago Health Sciences Campus in the CTRE clinic. In order to reduce participant burden, we will bank serum specimens from the screening visit. For those participants who provide written informed consent to enroll in the BBC and Vitamin D study, we will use this banked serum to measure 25(OH)D and 1,25(OH)2D using an LC/MS method at Quest. During the enrollment visit, participants will receive education about the study and the potential risks of participating and will provide written informed consent. The Loyola pharmacy will dispense the cholecalciferol and the calcium citrate to the enrolled participants.

Participants will then return at 6 and 12 weeks after the enrollment visit and participants will be instructed to fast at least four hours before the next visits. At the 6 and 12 week visit, a fasting blood specimen (15 ml) will be collected. Study staff will query participants about adverse effects and symptoms of vitamin D intoxication. Pill counts will be done at the 6 and 12 week visits. Participants will also collect their urine for 24 hours at the 12 week visit for measurement of urinary calcium excretion.

d. Randomization procedures-not applicable

This is a single arm non-blinded study.

Figure 1. Flowchart of study procedures

**e. Optional Biobanking.** Participants may *optionally* agree to reposit blood and urine samples into CRO-BIOREP (LU# 204853) for future research purposes. Participants will sign a second informed consent document should they agree to reposit their samples. The research team members and Biorepository staff will each retain a copy of the signed repository informed consent document. It is important to point out that participants do not need to agree to reposit samples in order to participate in the study.

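### Could the screening blood pressure, on which participants are selected, enter the repeated-measures ANOVA and bias the single-arm SBP change?

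*Combined protocol and SAP*

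**What the plan says.** The analysis of blood pressure is one sentence in section VIII: "Repeated measures analysis of variance models will be used to assess change in the outcome measures including systolic and diastolic blood pressure". The same sentence covers the vitamin D measures, parathyroid hormone and urine calcium. It gives no baseline, list of visits, contrast or significance level.

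Section V.d, item a (Blood pressure), sets the measurement times: "Seated blood pressure and pulse are measured at the screening visit, enrollment visit and at 6 and 12 week follow-up visits". Each visit's value is the mean of three readings. The schedule in G2 marks the same four occasions.

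Participants are selected on blood pressure. Inclusion criterion 10 requires SBP of at least 120 mmHg, and exclusion criterion 6 removes an average SBP of 140 mmHg or more. At screening, "Resting blood pressure will be taken per protocol and height and weight will be measured". Section VI.c then says "Once the lab values for the potential participant have been reported to the investigators, then study eligibility may be determined", and those found eligible are given an enrollment visit within 28 days.

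**The concern.** A reading used for selection makes a poor baseline. People admitted because one visit's SBP fell in a window will on average move back toward their own usual level at the next visit, treated or not. Averaging three readings minutes apart does not remove variation between visits. With a single arm, nothing in the data separates this drift from an effect of the supplements.

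Some of the protocol's wording could lead an analyst to the screening value. Section V.d lists it among the outcome measurements without reserving it for eligibility. A heading in G2 runs the screening and baseline visits together. The Abstract says "At baseline, all participants will have blood pressure measured and a fasting serum and 24-hour urine specimen will be collected", and section VI.c collects fasting blood and a 24-hour urine at screening. Baseline laboratory values also come from the screening draw, so a single baseline rule for everything in the section VIII sentence would point there.

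Change in blood pressure is part of aim b, and the data are meant to help design a larger randomized trial. At stake is a shifted planning estimate for SBP.

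**Working it through.** **The plan's own figure.** The only quantitative design figure is in Table 2: the chance of seeing at least one adverse event with n = 15. The formula 1 − (1 − p)^15 gives 0.965, 0.794 and 0.537 for p = 20%, 10% and 5%, against the stated 0.96, 0.79 and 0.54. It reproduces, and blood pressure plays no part in it.

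**Inputs.** From the protocol: one arm, n = 15, SBP window 120 to under 140 mmHg, four measurement occasions. Assumed, because the protocol gives none of them: source-population mean μ of 115 to 135 mmHg, SD 12 mmHg, between-visit correlation ρ of 0.6 to 0.8 and equal for all pairs of visits, a 5% test, no treatment effect. The diastolic limits are not modeled.

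**Expected null change from screening.** With a = (120 − μ)/12 and b = (140 − μ)/12, the mean of those selected is μ + 12 × [φ(a) − φ(b)]/[Φ(b) − Φ(a)]. The expected later change is −(1 − ρ) × (selected mean − μ).

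For μ = 120, a = 0 and b = 1.667. The excess is 12 × (0.3989 − 0.0995)/(0.9522 − 0.5) = 7.95, so the selected mean is 127.95. The change is −0.4 × 7.95 = −3.2 at ρ = 0.6 and −0.2 × 7.95 = −1.6 at ρ = 0.8.

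| Source mean | Mean of those selected | Change at ρ = 0.6 / 0.7 / 0.8 (mmHg) |
|---|---|---|
| 115 | 127.0 | −4.8 / −3.6 / −2.4 |
| 120 | 127.9 | −3.2 / −2.4 / −1.6 |
| 125 | 129.0 | −1.6 / −1.2 / −0.8 |
| 130 | 130.0 | 0 / 0 / 0 |
| 135 | 131.1 | +1.6 / +1.2 / +0.8 |

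The window is closed at both ends, so even the direction depends on a mean that the protocol does not give.

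**Effect on the ANOVA.** In 20,000 simulated null trials per scenario at μ = 120, with ρ = 0.6 / 0.7 / 0.8, the F test rejects in 18.3 / 14.8 / 10.9% with all four visits. With screening, week 6 and week 12 it rejects in 20.3 / 15.8 / 11.6%. With enrollment, week 6 and week 12 it rejects in about 5%.

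**Precision.** At μ = 120 the mean 95% half-width for the 12-week change is 5.4 / 4.8 / 4.0 mmHg from screening and 5.8 / 5.1 / 4.1 mmHg from enrollment. At each correlation it exceeds the corresponding bias from screening of 3.2 / 2.4 / 1.6 mmHg.

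**Which baseline the text points to.** Four places favor enrollment:

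- The Study forms list has one blood pressure form, for enrollment, week 6 and week 12.
- G2 repeats blood pressure at enrollment although that visit's laboratory tests use screening blood. Pressure would have little reason to be repeated if screening were the baseline.
- The Abstract describes a baseline followed by repeat visits at 6 and 12 weeks, and Safety Monitoring (G6) uses the same three occasions.
- Visit Frequency places the first urine collection at enrollment, which undercuts reading the Abstract's baseline as screening.

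On the other side stand the G2 heading and the bare listing in section V.d. The listing only records when pressure is measured and does not call the screening value a baseline. No passage makes screening the analysis baseline.

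**The case for a change.** The best case for acting is that a list of forms is not an analysis rule. Section VIII permits two different models, the choice could be made after the data are seen, and naming the baseline would take a sentence. A wide interval also does not reveal that its center has moved. Under the assumptions above, the shift could be close to the within-arm falls of 3.4 and 4.0 mmHg that the background section cites from an earlier vitamin D trial.

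Much of this stands. The omission is real, the arithmetic is sound under its assumptions, and the loose use of the word baseline, including the two timings for the first urine collection, is untidy. It remains a missing detail that the forms and schedule already lead an analyst to fill sensibly. It is not a planned biased analysis.

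Naming enrollment would also gain less than it first appears. The 5% rejection rate and the absence of bias rest on equal correlations between visits. If correlation with screening were 0.8 at enrollment and 0.6 at week 12, the null change from enrollment at μ = 120 would be −(0.8 − 0.6) × 7.95 = −1.6 mmHg. With 0.65 at week 12 it would be −1.2 mmHg.

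G2 also marks an eligibility check at enrollment. If that check re-applied the pressure limits, a fall of 0.9 to 2.1 mmHg from enrollment would remain at μ = 120. This is unlikely, since the inclusion/exclusion form is completed before enrollment only and section VI.c settles eligibility beforehand.

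**Conclusion.** The concern is right that section VIII leaves the blood pressure baseline unnamed, but it does not call for a change. The natural reading of the forms and schedule is enrollment, week 6 and week 12, which is the analysis the concern would ask for.

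The possible bias if screening were used instead runs from a fall of 4.8 mmHg through zero to a rise of 1.6 mmHg over source means of 115 to 135, given SD 12, equal correlations of 0.6 to 0.8 and no treatment effect. None of those inputs is in the documents.

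The consequence is limited under either reading. This is a 15-person feasibility pilot sized on adverse events, with no significance level or blood pressure decision rule. Time and habituation effects stay uncontrolled in a single arm whichever baseline is used, so its SBP change cannot isolate a treatment effect.

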As discussed by the Institute of Medicine, 25(OH)D levels > 20 ng/ml are likely sufficient for the majority of U.S. adults, especially if calcium intake is adequate because the main physiologic action of vitamin D is to increase absorption of dietary calcium. While clinical trials have demonstrated that calcium supplementation modestly reduces both systolic (SBP) and diastolic blood pressure (DBP), especially for adults less than 35 years of age, clinical trials of vitamin D supplementation for blood pressure lowering have shown mixed results with most trials showing no association between vitamin D supplementation and blood pressure change. Forman et al completed a 4-arm double blind placebo controlled 3-month trial of 1000, 2000, or 4000 IU of vitamin D3 per day vs. placebo in African-Americans with a median age of 51 years. The difference in SBP between baseline and 12 weeks was 1.7 mmHg for the placebo group, -0.66 mmHg for the 1000 IU/d group, -3.4 mmHg for the 2000 IU/day group, and -4.0 mmHg for the 4000 IU/day group. Each 1 ng/ml increase in plasma 25(OH)D was associated with a 0.2 mmHg decline in SBP levels (P=0.02) if baseline 25(OH)D level was < 20 ng/ml. It should be noted that in this trial, all participants were given 200 mg of calcium daily and baseline calcium intake was not assessed.

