## V. Study Design

a. This will be a single arm non-blinded study of 15 participants.

b. The study population will consist of 15 adults ages 25-45 years with self-reported African American race/ethnicity. The study will be conducted during a 4 month window to eliminate the seasonal effects on vitamin D levels. All participants will provide written informed consent after study investigators ensure that potential participants meet all eligibility criteria outlined below.

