### c. Sample size determination

This pilot study will collect data to design a larger randomized clinical trial. The sample size of 15 participants will allow us to detect adverse events which occur at a rate  $\geq$  20% with 96% probability. We will have a 79% probability of detecting complication rates  $\geq$  10%. We will have moderate probability to detect adverse events which occur in 5% or less of participants. As a small pilot study, we will determine the tolerability of taking 5,000 IU of Cholecalciferol with 1000 mg elemental calcium daily for 12 weeks and will examine changes in measures of vitamin D status including total 25(OH)D, free 25(OH)D levels and PTH levels.

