Free 25(OH)D levels-will be measured using kits from Quest. The free 25(OH)D ELISA is based on a two-step immunoassay procedure performed in a microtiter plate. During the first incubation step, free 25(OH)D (including both 25(OH)D2 and D3) is bound to the antivitamin D antibody coated on the wall of the microtiter plate. The in vivo equilibrium between free and bound 25(OH)D is minimally disturbed. After washing, a fixed amount of biotinylated 25(OH)D is added to each well. The nonbound biotinylated 25(OH)D is removed by washing, and a streptavidin peroxidase conjugate is added. In a next step, a 3', 5, 5'-tetramethylbenzidine chromogenic substrate is added. Finally, the reaction is stopped by the addition of a stop reagent and the absorbance (A450 nm) is measured using a plate spectrophotometer. The concentration of free vitamin D in the sample is inversely proportional to the absorbance in each sample well. Free vitamin D will be measured in banked specimens obtained at the screening visit and in blood specimens obtained at 12 weeks after enrollment.

d. Parathyroid hormone (PTH) levels

Intact PTH levels will be measured with the use of the Elecsys Parathyroid Hormone Immunoassay (Modular Analytics E170, Roche Diagnostics) (inter-assay coefficient of variation, 2.5%). PTH levels will be measured by Quest. PTH levels will be measured in banked specimens obtained at the screening visit and in blood specimens obtained at the visit 12 weeks after enrollment.

e. Calcium and creatinine

Serum and urine calcium and creatinine will be measured using colorimetric assays from Roche Diagnostics by Quest. Creatinine will be measured in serum collected at the screening visit. Serum calcium will be measured from specimens collected at the screening visit and at 6 and 12 weeks of follow-up after starting the enrollment visit.

f. Calcium intake-calcium intake will be estimated at baseline only using an online interactive calcium calculator from the International Osteoporosis Foundation <http://www.iofbonehealth.org/calcium>

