## Early withdrawal of subjects

A subject may withdraw from the study anytime he/she wishes. Any participant who withdraws from the study along with their reasons for withdrawing from the study will be reported to the Loyola Institutional Review Board.

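### No rule for missed visits: repeated measures ANOVA would by default drop incomplete participants from a study of 15, and a mixed model would reduce the loss

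*Combined protocol and SAP*

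**What the plan says.** The whole plan for analysing change is one sentence in Section VIII: "Repeated measures analysis of variance models will be used to assess change in the outcome measures including systolic and diastolic blood pressure". The same sentence covers the vitamin D measures, PTH and 24-hour urine calcium. It does not give an estimation method, a covariance structure, a baseline visit or a rule for missed visits. The documents mention no mixed model, no imputation and no expected dropout rate.

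Other sections bear on this:

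- Section V, Study Design: "This will be a single arm non-blinded study of 15 participants".
- Study outcomes, blood pressure: "Seated blood pressure and pulse are measured at the screening visit, enrollment visit and at 6 and 12 week follow-up visits". Two of these four readings precede treatment. The list of study forms has a blood pressure form for enrollment and weeks 6 and 12, which hints that enrollment is baseline, but the Analysis Plan does not say so.
- Study outcomes, parathyroid hormone: "PTH levels will be measured in banked specimens obtained at the screening visit and in blood specimens obtained at the visit 12 weeks after enrollment". Free 25(OH)D and 1,25(OH)2D are likewise measured twice, as is urine calcium by the schedule of visits. Total 25(OH)D is scheduled three times.
- Early withdrawal: "A subject may withdraw from the study anytime he/she wishes". Reasons go to the ethics board; the consequence for the analysis is not addressed.
- Stopping plans: participants who meet a stopping rule "will stop treatment but they will continue to be monitored in the study through week 12".

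**The concern.** Classical repeated measures ANOVA needs a complete row for each participant. With no other rule stated, someone who attends enrollment and week 12 but misses week 6 leaves the analysis altogether, and so does someone who withdraws after week 6. With 15 people, each such loss is visible in the result.

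The study is meant to supply data for designing a larger trial of blood pressure lowering. Its mean change, SD of change and within-person correlation are therefore what it hands on. Listwise deletion makes these less precise. If those who miss visits differ from those who attend, it can also shift the mean change.

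**Working it through.** **Inputs from the documents.** n = 15, one arm. Blood pressure is taken before treatment and at weeks 6 and 12. For illustration only, the true systolic change is set to the fall of "4.0 mmHg for the 4000 IU/day group" that Background and Significance reports from a cited four-arm trial.

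**Assumptions (the documents give none of these).** Systolic SD 10 mmHg; equal between-visit correlation of 0.5 to 0.7; 5% to 20% missing, independently, at each of the two follow-up visits; three analysis visits (0, 6 and 12 weeks), since enrolled participants should have their pre-treatment readings.

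**The plan's own figure.** The sample size section rests on adverse events: "The sample size of 15 participants will allow us to detect adverse events which occur at a rate" of at least 20% with 96% probability. With 1 − (1 − p)^15, rates of 20%, 10% and 5% give 0.9648, 0.7941 and 0.5367, against 0.96, 0.79 and 0.54 in Table 2. It reproduces. It says nothing about blood pressure and makes no allowance for missing data.

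**Step 1: participants left.** Expected complete cases are 15(1 − m)². The chance that all 15 are complete is (1 − m)^30.

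| Missing per follow-up visit, m | Complete cases | Chance all 15 complete |
|---|---|---|
| 5% | 13.5 | 21% |
| 10% | 12.2 | 4% |
| 15% | 10.8 | 0.8% |
| 20% | 9.6 | 0.1% |

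**Step 2: what a mixed model recovers.** Take correlation 0.6 and 3 of 15 incomplete. With n complete pairs, SE = 10 × √(2(1 − 0.6)/n).

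- Full data, n = 15: 2.31. Complete cases, n = 12: 2.58. The ratio is √(15/12) = 1.118, whatever the correlation.
- Mixed model, three missed week 6 only: all 15 baseline and week-12 pairs remain, so the SE is 2.31 and the loss is fully recovered.
- Mixed model, three missed week 12 only: regressing week 12 on the two earlier visits gives coefficients 0.6/1.6 = 0.375 and residual variance 100 × (1 − 2 × 0.36/1.6) = 55. The variance of the change is 55/12 + 25/15 = 6.25, where 25 = 100 × (0.625² + 0.375² − 2 × 0.625 × 0.375 × 0.6). The SE is 2.50, so (2.58 − 2.50)/(2.58 − 2.31), about 30% of the loss, is recovered.
- Mixed model, three missed both: 64/12 + 16/15 = 6.40, SE 2.53, about 19% recovered.

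**Step 3: both kinds of missed visit together.** Simulation at correlation 0.5, 4,000 trials per setting:

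| Missing per visit | Complete-case SE | Mixed-model SE | Ratio |
|---|---|---|---|
| 10% | 2.94 | 2.74 | 1.07 |
| 15% | 3.04 | 2.74 | 1.11 |
| 20% | 3.28 | 2.81 | 1.17 |

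Ratios at correlation 0.7 are similar.

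**Step 4: bias.** Correlation 0.6, true change −4 mmHg, about 3 of 15 missing week 12, 2,000 to 2,500 runs per row (Monte Carlo error about 2.6/√2500 = 0.05 mmHg, slightly more with 2,000 runs):

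| Week-12 missingness driven by | Complete-case bias | Mixed-model bias |
|---|---|---|
| Observed week-6 change | −0.97 | −0.03 |
| Observed baseline level | +0.78 | −0.04 |
| Unseen week-12 change | −1.92 | −1.35 |
| Unseen week-12 level | −0.90 | −1.19 |

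When data were missing completely at random, neither method was materially biased. Missingness driven by the observed week-6 level also left both almost unbiased.

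**The case against.** The strongest reply is that the plan never says incomplete participants are dropped, and that the term repeated measures ANOVA is sometimes used for a mixed-model fit. That is correct: deletion is the default of the classical method, not a stated rule of this plan. It narrows the point but does not remove it, because a reader cannot tell which analysis is meant.

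A second reply is that the precision gain is modest and needs no mixed model. In a 6,000-run simulation at correlation 0.5, simply using every available baseline and week-12 pair gave SEs of 2.79, 2.80 and 2.97 at 10%, 15% and 20% missing. Complete cases gave 2.94, 3.06 and 3.34, and the mixed-model estimate 2.75, 2.73 and 2.86. Available pairs therefore close 77% to 79% of the gap here (up to 84% across correlations 0.5 and 0.7). This stands for precision. It does not help with bias: in Step 4 only week 12 goes missing, so the available pairs and the complete cases are the same people.

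Third, this is a 12-week feasibility study with payment for each visit, sized on adverse events, with no power claim for blood pressure. Participants who stop treatment stay in follow-up, so stopping does not itself create missing data. All of this stands. Missing data would come from missed visits and voluntary withdrawal, and the documents do not say how common these will be.

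A reader might also infer that people without benefit will leave, so that the fall in blood pressure is exaggerated. The documents do not support a direction: they promise participants their laboratory results but do not say they are told their blood pressure change, and missingness driven by baseline pressure gave the opposite sign. Nor is sphericity a reason to switch. A random intercept imposes compound symmetry, which is a stricter assumption.

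**Conclusion.** The point holds in a limited form. The plan names a method whose classical version discards incomplete participants, gives no rule for missed visits, and leaves the baseline blood pressure visit undefined. Under the assumed 10% to 20% missing per follow-up visit, about 12 to 10 of 15 remain and the SE of the week-12 change is about 7% to 17% larger than with a mixed model. Bias of up to about 1 mmHg, of either sign, is possible when missingness depends on observed values. That is about a quarter of the illustrative 4.0 mmHg fall, but well under one SE (0.97 against about 2.6).

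It would go too far to conclude that a mixed model avoids the problem. It recovers about 30% of the SE loss for a missed week 12, and has no intermediate visit to draw on for outcomes measured twice. It remains biased when missingness depends on unseen week-12 values, in one scenario slightly more than complete cases. No stated power or hypothesis claim is affected; what is at stake is the quality of the estimates passed to the larger trial. The sizes rest on assumed missingness, SD and correlation. The gap in the plan does not.

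**What to change.** Replace the sentence in Section VIII with text to this effect: change in each outcome will be estimated with a likelihood-based linear mixed model using all observed visits, with visit as a categorical fixed effect, a simple covariance structure (for example a participant random intercept) and Kenward-Roger degrees of freedom. State whether the screening or the enrollment reading is the blood pressure baseline.

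Report mean change at weeks 6 and 12 (week 12 only for outcomes measured twice) with 95% confidence intervals, the SD of change, the within-person correlation, and the number missing at each visit with reasons. Take the SD of change from the observed pairs, because a random-intercept model forces it to be equal at weeks 6 and 12. A short sensitivity analysis that shifts the unobserved week-12 values would be a useful addition, since the mixed model does not protect against missingness that depends on them.

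The cost is wording and a different fitting procedure, with no new visits or data. With complete data the mean changes are the same as under the current plan. The one downside is that 15 participants support only a simple covariance structure.
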